The eligible PIBD cases will comprise all incident cases of PIBD over the last decade, we will not follow patients up beyond 01/01/2020 due to changes in patient health behaviour and primary care interactions due to COVID-19. We will extract sociodemographic details for all these cases and matched controls (described below). Sociodemographic data will comprise by age group, gender, ethnicity, and socioeconomic status. Ethnicity will be categorised as follows to be consistent with the UK official census categories: White, Asian, Black African/Caribbean, Mixed, and Other. The index of multiple deprivation (IMD) will be used as a measure of socioeconomic status. This is derived from patient postcode at the point of data extraction.

Stream 1: Definition of matched controls without IBD

We will match each incident case of PIBD with controls (children without IBD) using propensity score matching (matching on the sociodemographic variables list above and matching within primary care practice if numbers allow). People with a known diagnosis of irritable bowel syndrome (IBS) will be excluded from the potential pool of controls. We will compare the incidence of new onset mental health conditions in PIBD and controls using a similar approach to that used by Butwick et al. (2019) in their paper exploring psychiatric disorders in a

PIBD cohort in Sweden.(9) The mental health conditions to be examined are listed in table 1 although there is scope to add to or modify these in discussion with the study authors. For a composite 'any psychological condition' outcome (see Table 1), risk will be stratified by age of PIBD onset and sex.

We will then go beyond the analysis of the Swedish study to estimate the cumulative risk of the 'any psychological condition' composite outcome in PIBD patients compared with controls. This will provide a unique, robust, estimate of the overall mental health burden (prevalence) in PIBD.

Condition	Description
Primary outcomes	
Any psychological condition	A composite of all the chronic psychiatric conditions listed below* (depression, anxiety, eating disorders, body image disorder, attention-deficit disorder, behavioural disorders, adjustment disorder, acute stress disorder, and post-traumatic stress disorder)
Depression	Major recurrent depression or treated depressive episode
Anxiety	Non-phobia related anxiety episodes or disorder
Secondary outcomes	
Self-harm	Any coded episode of deliberate self-harm of any type

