Suicide attempt	Any episode of suicide attempt and suicide related codes, including deliberate medication overdose
Other chronic psychiatric conditions	Eating disorders, body image disorder, attention-deficit disorder (ADHD), behavioural disorders, adjustment disorder, acute stress disorder, schizophrenia, bipolar disorder and post-traumatic stress disorder (PTSD)
Others	Problems with sleep

*this excludes conditions which are potentially single events i.e. self-harm or suicide attempt. (See Appendix 1 – Table s3 for Read Codes and SNOMED Codes

for mental health conditions, Table s4 for mental health condition algorithms and Table s5 for WHO ICD-10 mental health conditions).

Stream 1: Incidence of mental health conditions

The study will report the incidence of each mental health condition overall in the PIBD cases and controls, and adjusted hazard ratios to test the association between PIBD and risk of the same mental health conditions. Within the PIBD cohort we will examine the relationship between PIBD age of onset, sex, ethnicity, and social deprivation and the 'any psychological condition' composite outcome.

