Cox proportional hazards models will be used to compare disease incidence in PIBD cases and controls and also when comparing the associations of baseline features and outcomes within the PIBD cohort. The study start date will be the date of diagnosis of PIBD or, for controls, the date of diagnosis of their matched counterpart. The end of follow-up will be the first of; the point of data extraction (**exact date TBC**), the patient's 25th birthday, date of loss to follow-up (either GP practice deregistration or death). All individuals contributing at least six months of follow-up time in the analysis will be included. Those with existing evidence of the mental health condition prior to baseline will be excluded for analysis of that particular outcome where it would not reoccur, for example if individual has already received a diagnosis of recurrent depressive disorder they would not receive this diagnosis again, although conditions at baseline that can reoccur, such as suicide attempt, would not be excluded. Models will be adjusted for age, gender, socioeconomic status, ethnicity, and other childhood conditions (asthma, atopic dermatitis, allergic rhinitis, thyroid disease, epilepsy, diabetes, cancer, juvenile idiopathic arthritis (JIA) including systemic JIA, systemic lupus erythematosus (lupus), ankylosing spondylitis (AS) and psoriatic arthritis). Statistical significance for analyses will be reported using P values and 95% confidence intervals as appropriate.

Cumulative risk (i.e. prevalence) of the 'any psychological condition' composite outcome will be evaluated up to age 25. Cumulative incidence will be calculated by using methods to estimate risk similar to those recently published when assessing lifetime risk of other chronic conditions in the Lancet.(11, 12) Key outputs will be cumulative risk plots, presenting the cumulative incidence of the outcome by age for PIBD patients compared to controls. At a particular age, the cumulative incidence estimate can be interpreted as the lifetime incidence of the outcome up until the year of age in question. Childhood cumulative risk will be defined as the cumulative incidence at age 18.

Stream 1: Sensitivity analysis

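### Stream 1 aims at new-onset conditions, but its exclusion rule keeps people with earlier depressive episodes or anxiety, and its event definitions can date past illness as a new event

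*Combined protocol and SAP*

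**What the plan says.** The aim is set in 'Stream 1: Definition of matched controls without IBD': "We will compare the incidence of new onset mental health conditions in PIBD and controls".

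The risk set is defined in 'Stream 1: Incidence of mental health conditions'. People with earlier evidence of a condition "will be excluded for analysis of that particular outcome where it would not reoccur". One example is given on each side. Recurrent depressive disorder leads to exclusion, while "conditions at baseline that can reoccur, such as suicide attempt, would not be excluded".

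Table 1 defines the primary depression outcome as "Major recurrent depression or treated depressive episode", and the primary anxiety outcome likewise covers episodes or disorder. The composite is "A composite of all the chronic psychiatric conditions listed below", and its footnote adds that "this excludes conditions which are potentially single events i.e. self-harm or suicide attempt".

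Controls are selected by propensity score, "matching on the sociodemographic variables list above": age group, gender, ethnicity and socioeconomic status. For the Cox analysis, "Models will be adjusted for age, gender, socioeconomic status, ethnicity, and other childhood conditions"; the conditions then listed are all physical.

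Appendix 2 gives the codes (sTable 2.1) and the algorithms (sTable 2.2). A depressive episode or anxiety needs a code with concurrent treatment. Recurrent depressive disorder needs either a depressive code more than one year old with current treatment, or any recurrent-disorder code by itself.

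**The concern.** Two things decide an incidence analysis: who is at risk at the start, and what counts as an event afterwards. Both are open to past illness here, in outcomes the plan calls primary.

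If people with an earlier episode stay in, a relapse counts the same as a first onset. Because mental health history is neither matched nor modelled, any difference in history between PIBD cases and controls passes into the hazard ratio. If codes recording a past or remitted illness count as events, an old episode noted at a later consultation is dated as new. Two analysts could follow the text and build different risk sets for depression, anxiety and the composite.

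The age curve has a related gap. It is called both prevalence and lifetime incidence, although the only stated start date is PIBD diagnosis or the matched date.

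**Working it through.** The plan states no event count, baseline prevalence or recurrence rate, so there is no figure to reproduce. The check sets the sections side by side, counts code rows, and adds one illustration on assumed inputs.

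**1. Who is kept**

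| Stream 1 outcome | Prior cases under the stated rule |
|---|---|
| Recurrent depressive disorder | Excluded (named example) |
| Treated depressive episode | Not named; can recur, so kept on a literal reading |
| Anxiety | Not named; can recur, so kept on a literal reading |
| Composite | Not classified; the chronic wording and footnote lean towards exclusion |
| Suicide attempt | Kept (named example) |
| Self-harm | Not named; kept by the same logic |

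**2. Event rows that describe past or remitted illness** (rows for psychosis in remission not counted)

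| List | History or past | Full or unqualified remission | Partial remission |
|---|---|---|---|
| sTable 2.1, depressive episode | 1 | 7 | 8 |
| sTable 2.1, anxiety | 1 | 0 | 3 |
| sTable 3.1, recurrent depressive disorder | 0 | 6 | 5 |
| sTable 3.1, parasuicide | 3 | 0 | 0 |

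- Depression: 7 + 8 = 15 remission rows (3 Read V2, 4 CTV3, 8 SNOMED), plus SNOMED 161469008 for history.
- Anxiety: 161470009 for history; 16265301000119100, 53956006 and 63909006 for partial remission.
- Recurrent depression: 6 + 5 = 11 remission rows (3 Read V2, 2 CTV3, 6 SNOMED).
- Parasuicide: 146A., 161474000 and 23233009.

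**3. What sTable 2.2 does with them**

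- *Depressive episode and anxiety.* Concurrent treatment is required. This limits the problem but does not remove it: treatment may be continuing from an episode that began before index.
- *Recurrent depression, code arm.* No treatment is needed. The only list with that heading is in sTable 3.1, so its 11 remission rows would each qualify alone.
- *Recurrent depression, treatment arm.* Suppose one episode is coded two years before index and treatment is current after index. The old code and the treatment together meet the definition after index. The exclusion does not clearly prevent this, because one earlier episode is not yet recurrent disorder.
- *Suicide attempt.* sTable 2.1 has no list for it. If the sTable 3.1 parasuicide list is used, its 3 past-attempt rows count as new attempts, since prior attempts are kept and no treatment is required.

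**4. Direction of any bias (all inputs assumed)**

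Let p1 and p0 be the shares with prior illness in cases and controls, and r the recurrence rate divided by the first-onset rate. With prior cases kept, the rate ratio early in follow-up is HR × (1 − p1 + p1·r) / (1 − p0 + p0·r).

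- No effect, equal shares: 1.00 for any r.
- No effect, 10% v 5%: r = 3 gives 1.20/1.10 = 1.09; r = 10 gives 1.90/1.45 = 1.31.
- No effect, 5% v 10%: 1.10/1.20 = 0.92; 1.45/1.90 = 0.76.
- Equal share p, true HR 1.5 on first onset only: [1.5(1 − p) + p·r] / [(1 − p) + p·r]. For p = 5%, r = 3 this is 1.575/1.10 = 1.43; for p = 20%, r = 10 it is 3.2/2.8 = 1.14.

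The ratio can move either way, and the documents do not say which of these cases applies.

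**5. The age curve**

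Cumulative incidence counts everyone with onset by a given age; point prevalence counts those ill at that age. The calculation described is cumulative incidence. A lifetime reading would also need onsets before diagnosis, and the plan does not say whether these are counted or whether people enter the curve at their index age.

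**The case against.** The plan does state a principle, namely whether the condition can recur, with an example on each side, so it is not silent. That stands. What is missing is an outcome-by-outcome classification, and the literal result conflicts with the new-onset aim.

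The treatment requirement protects the depressive-episode and anxiety definitions to a real extent. That stands too. A reader might infer that the recurrent rows within the sTable 2.1 depressive-episode list also count untreated. The documents do not show this: that list falls under the code-plus-treatment rule, and the list headed as recurrent disorder is the one in sTable 3.1.

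The appendix is visibly unfinished, and the main text says a diagnostic algorithm will be developed. sTable 2.3 defines self-harm, including suicide attempt, by ICD-10 codes. A reader might infer that old attempts will be counted as new; the documents support this only if the quality-of-life list is reused for Stream 1. Both outcomes are secondary.

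Finally, prevalence is a label. For an ever-affected reading of chronic conditions it is not far from lifetime prevalence, and the curve methods are delegated to cited papers. The wrong word does not make the planned calculation wrong, but the handling of pre-index onsets still has to be stated in the plan.

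**Conclusion.** The point holds as a fault in the risk set and event definitions of the primary Stream 1 outcomes, and should be fixed before the cohort and event files are built. For depression and anxiety this goes beyond missing detail: followed as written, the definitions admit events that are not new onset.

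What can be counted is the number of rows: 16 for depression and 4 for anxiety in sTable 2.1, 11 in the recurrent-depression list, and 3 in the parasuicide list if it is used. How often these codes are entered is not given.

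A reader might infer that the hazard ratio is biased upwards. The documents do not support any size or direction. The ranges in the working rest wholly on assumed shares and recurrence rates, and equal history with no effect gives 1.00. The prevalence wording is a labelling error, with a separate unstated choice about onsets before index.

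**What to change.** 1. **Risk set.** For depression, anxiety and the composite, exclude from both groups anyone with the condition recorded before index (for the composite, any component). Count as prior evidence either the code-plus-treatment algorithm, or any pre-index 'history of' or 'in remission' code with or without treatment. Run exclusion on any prior code as a sensitivity analysis, and report numbers excluded by group.
2. **Events.** Do not count 'history of', 'H/O', 'previous known' or full-remission codes (including unqualified remission) as incident events, in sTable 2.1 or in the sTable 3.1 recurrent-depression and parasuicide lists if these are used. Count partial-remission codes only in people with no earlier record, since a true onset may first be coded that way, and leave them out in a sensitivity analysis. Treat a history code entered after index as neither an event nor a reason to change baseline status. For recurrent depression, require the qualifying episode code to be dated after index.
3. **Self-harm and suicide attempt.** Keep prior cases, adjust for or stratify by history recorded before index, and name the code list used.
4. **Age curve.** Delete prevalence in both places. Either use delayed entry at index and label the result as risk after PIBD diagnosis among those free of the condition (for controls, after the matched date), or keep the lifetime label only if pre-index onsets are counted in both groups.

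The cost is protocol wording, a review of 16 + 4 + 11 + 3 = 34 rows (some codes appear in more than one list), and one covariate. The look-back is feasible for most: 'Project highlights' says the majority of the paediatric population have full records from birth. The downside is somewhat fewer people and events in the primary models; a lifetime curve would also be limited to people with complete records.

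### Stream 1 keeps people with earlier psychiatric history but neither matches nor adjusts for it, so if history is unbalanced at index the single-condition hazard ratios can carry pre-index differences

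*Combined protocol and SAP*

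**What the plan says.** The section on matched controls without IBD describes the Stream 1 comparison as one of new-onset mental health conditions. Controls are chosen by propensity score, "matching on the sociodemographic variables list above and matching within primary care practice if numbers allow". The list meant is in the preceding section on people with new-onset IBD: "Sociodemographic data will comprise by age group, gender, ethnicity, and socioeconomic status".

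The section on incidence of mental health conditions then sets the analysis:

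- Model: "Cox proportional hazards models will be used to compare disease incidence in PIBD cases and controls".
- Time zero: "The study start date will be the date of diagnosis of PIBD"; controls take the date of their matched case.
- Baseline rule: people who already have the condition "will be excluded for analysis of that particular outcome where it would not reoccur", with recurrent depressive disorder as the example. On the other side, "conditions at baseline that can reoccur, such as suicide attempt, would not be excluded". The remaining outcomes are not sorted into either class.
- Covariates: "Models will be adjusted for age, gender, socioeconomic status, ethnicity, and other childhood conditions". The bracketed list that follows runs from asthma to psoriatic arthritis and contains physical conditions only.

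The one Stream 1 sensitivity analysis concerns controls who are registered but do not attend their practice. It does not touch psychiatric history.

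**The concern.** Two kinds of earlier illness stay in the risk set. The first is history of the same outcome where that outcome can recur. Suicide attempt is named. Self-harm follows by the same logic, since sTable 2.3 defines it to include suicide attempt. Depressive and anxiety episodes arguably follow too, because Table 1 defines those primary outcomes partly as episodes. The second is history of a different condition, such as ADHD or an eating disorder when depression is the outcome.

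Neither kind is balanced by design or by the model. Anyone with such history is likely to have a higher hazard afterwards. The plan itself treats baseline mental health as informative: Stream 2 groups IBD patients by it and compares later affective symptoms, including self-harm, between the groups.

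At stake are the hazard ratios for depression and anxiety (primary outcomes) and for self-harm, suicide attempt and the other single conditions (secondary outcomes). If history is unbalanced at diagnosis, part of the ratio reflects what was already there, and a recurrence can be read as a new condition.

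**Working it through.** **Reading the text.** The documents state no sample size, event count, effect size or baseline prevalence of psychiatric history for Stream 1, so there is no planned figure to reproduce. Set side by side, the matching list (age group, gender, ethnicity, socioeconomic status, and practice if numbers allow), the covariate list (demographics and physical conditions) and the baseline rule leave psychiatric history handled only by the same-outcome exclusion, and only for conditions judged not to recur.

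The depression algorithm in sTable 2.2 adds to this. It counts a depressive code more than one year old, together with current treatment, as recurrent depressive disorder. On a plausible reading, a child with one depressive episode before index stays in the analysis and can later become an outcome partly because of that pre-index code.

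**Size of the mechanism, on assumed inputs.** Suppose IBD has no effect within levels of prior history, and prior history multiplies the hazard by h. With prevalence of history p1 in cases and p0 in controls, the unadjusted rate ratio is approximately

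[1 + p1(h − 1)] / [1 + p0(h − 1)].

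None of p1, p0 or h is in the documents; all are assumptions.

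| Outcome (history) | p1 | p0 | h | Ratio |
|---|---|---|---|---|
| Depression (other condition) | 10% | 6% | 3 | 1.20/1.12 = 1.07 |
| Depression (other condition) | 15% | 6% | 3 | 1.30/1.12 = 1.16 |
| Depression, equal history | 6% | 6% | 3 | 1.12/1.12 = 1.00 |
| Depression, reversed | 6% | 10% | 3 | 1.12/1.20 = 0.93 |
| Suicide attempt (prior attempt) | 1% | 0.5% | 10 | 1.09/1.045 = 1.04 |
| Suicide attempt (prior attempt) | 2% | 0.5% | 10 | 1.18/1.045 = 1.13 |
| Suicide attempt, reversed | 0.5% | 1% | 10 | 1.045/1.09 = 0.96 |

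A wider grid, with history twice as common in cases and h from 3 to 20, gives 1.04 to 1.28 (4% v 2%), 1.09 to 1.49 (10% v 5%) and 1.17 to 1.66 (20% v 10%).

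**Check by simulated Cox models.** There were 60,000 cases and 240,000 controls, a hazard of 1% a year without history, follow-up of up to 10 years, no true IBD effect and h = 5.

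- History 10% v 5%: formula 1.40/1.20 = 1.17; unadjusted hazard ratio 1.15; adjusted for history 0.997; restricted to people without history 1.004.
- History 20% v 10%: formula 1.80/1.40 = 1.29; unadjusted 1.27; adjusted 0.996; restricted 0.999.

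The formula slightly overstates the Cox result. Adjustment or restriction removes the distortion in this set-up. Adjusted fits at h = 10 failed numerically and are not used.

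**The case against.** The strongest reply is about what is being estimated. The Stream 1 objective is to compare risk in young people with IBD with that in population controls, not to isolate risk arising only after diagnosis. An obvious reason for imbalance at index is that IBD symptoms precede diagnosis. Earlier psychiatric illness may then be partly an early effect of undiagnosed IBD, and adjusting for it would remove part of the association of interest. This stands: it rules out making cross-condition adjustment the main model everywhere. It does not answer the retention of prior cases of the same outcome in a comparison described as new onset.

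The second reply is that imbalance is not shown. This also stands. A reader might infer that pre-diagnosis differences are in fact being reported as risk after IBD. The documents give no prevalence for either group, and with equal prevalence this distortion is absent.

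The third concerns scope. A reader might extend the point to the composite of any psychological condition. The natural reading of the exclusion rule removes people with any prior component condition from that analysis, so the composite is largely protected, although the plan does not say so. People with the same non-recurrent condition are also removed from that condition's analysis.

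**Conclusion.** The point holds for the single-condition outcomes and is conditional. The text establishes that history is retained, is not matched on and is not a covariate, and that this sits poorly with a new-onset comparison in which no list says which outcomes recur. Those findings need no assumed figure.

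The effect on the hazard ratios does need assumptions. It is an inflation of about 4% to 16% in the four scenarios with more history in cases, larger under the wider grid, nil if prevalence is equal, and an understatement if history is commoner in controls. Direction and size stay unknown until baseline history is tabulated. The documents do not support saying that the ratios are biased, that the composite is affected to the same degree, or that a history-adjusted model should replace the planned one.

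**What to change.** 1. State for each Table 1 outcome whether it counts as recurrent under the baseline rule, including depressive and anxiety episodes and self-harm, and say how the rule applies to the composite.
2. Report psychiatric history before the index date in PIBD cases and controls, with the lookback stated. The project highlights say records since birth exist for most of the paediatric population.
3. For outcomes where prior cases are retained, either analyse first-ever events or add prior history of that outcome as a covariate, and show the result without this step alongside.
4. For depression, anxiety and the other single-condition outcomes, add a sensitivity model adjusted for any other prior Table 1 psychiatric condition, leaving out sleep problems. Present it next to the planned model, with a note that part of the pre-diagnosis illness may be an early effect of undiagnosed IBD.

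The history variables reuse condition codes that the study needs anyway for its outcomes. The cost is a baseline table and a few extra result rows. A first-ever definition would also reduce the number of events, which matters most for suicide attempt and self-harm.
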